9.2 Method and Timing

Patients will undergo their initial response assessment by CT scans between weeks 12-14 after initiation of -PD1/PDL1 immune checkpoint inhibitor, every 12-14 weeks thereafter until progression, or as clinically indicated per institutional standards. The response assessments will not be read in real time. The formal reads of the response assessments will be completed once there is a statistically valid endpoints assessment at the end of trial accrual.

9.3 Other Response Parameters

Immune correlative studies will be performed on bio-specimens collected and is outlined in the study schema and calendar. The time-points of blood collection will be at baseline, while on nelfinavir only, after the first dose of PD1/PDL1 immune checkpoint inhibitor, post-radiation treatment, 1 month (+/- 2 weeks) after taking Nelfinavir, and 6 months (+/- 2 weeks) from enrollment (see Appendix 14.4 Treatment Calendar).

10.0 DATA MANAGEMENT/CONFIDENTIALITY

The investigator will ensure that data collected conform to all established guidelines. Each subject is assigned a unique patient number to assure subject confidentiality. Subjects will not be referred to by this number, by name, or by any other individual identifier in any publication or external presentation. The licensed medical records department, affiliated with the institution where the subject receives medical care, maintains all original inpatient and outpatient chart documents.

11.0 STATISTICAL CONSIDERATIONS

11.1 Sample Size with Power Justification

The primary objective of this study is to evaluate the response rate in patients with non-small cell lung cancer (NSCLC), melanoma, or renal cell carcinoma (RCC) treated with nelfinavir, radiation therapy and anti-PD-1/PD-L1 therapy. Evaluation of this investigational therapy will be done in disease-specific cohorts separately evaluated by patients naïve to anti-PD-L1/PD-L1 therapy and those with disease refractory to anti-PD-1/PD-L1 therapy.

The total sample size for this study is 20 patients in each of the 6 cohorts (3 disease type by 2 anti-PD-1/PD-L1 exposure groups) for a total of 120 patients evaluable for response. The expected accrual rate is 30 patients per year. The design within each cohort is a single arm, single stage design. The sample size justification for each of the cohorts is follows. Sample size calculations were done using this calculator: <https://stattools.crab.org/Calculators/oneArmBinomial.html>.

Non-Small Cell Lung Cancer (NSCLC):

1. Checkpoint Naïve: In this cohort a true response rate of 50% or greater would be considered evidence of activity whereas a response rate of 25% or less (based on historical data) would not be considered of interest. With 20 patients, this study has 86% power to rule out a response rate of 25%, at the 1-sided 0.10 level if the true response rate were 50%. The observation of at least 8 responses (8/20; 40% ORR) would be

considered evidence to rule out a response rate of 25%. The exact power and type I error for this design are 87% and 10%, respectively.

2. Checkpoint refractory: In this cohort a true response rate of 25% or greater would be considered evidence of activity whereas a response rate of 5% or less (based on historical data) would not be considered of interest. With 20 patients, this study has 91% power to rule out a response rate of 5%, at the 1-sided 0.10 level if the true response rate were 25%. The observation of at least 3 responses (3/20; 15% ORR) would be considered evidence to rule out a response rate of 5%. The exact power and type I error for this design are 91% and 7.6%, respectively.

Melanoma:

3. Checkpoint Naïve: In this cohort a true response rate of 68% or greater would be considered evidence of activity whereas a response rate of 43% or less (based on historical data) would not be considered of interest. With 20 patients, this study has 84% power to rule out a response rate of 43%, at the 1-sided 0.10 level if the true response rate were 68%. The observation of at least 11 responses (11/20; 55% ORR) would be considered evidence to rule out an rate of 43%. The exact power and type I error for this design are 93% and 19.5%, respectively.
4. Checkpoint refractory: In this cohort a true response rate of 40% or greater would be considered evidence of activity whereas a response rate of 15% or less (based on historical data) would not be considered of interest. With 20 patients, this study has 90% power to rule out a response rate of 15%, at the 1-sided 0.10 level if the true response rate were 40%. The observation of at least 5 responses (5/20; 25% ORR) would be considered evidence to rule out an response rate of 15%. The exact power and type I error for this design are 95% and 17%, respectively.

Renal Cell Carcinoma:

5. Checkpoint Naïve: In this cohort a true response rate of 50% or greater would be considered evidence of activity whereas a response rate of 25% or less (based on historical data) would not be considered of interest. With 20 patients, this study has 86% power to rule out a response rate of 25%, at the 1-sided 0.10 level if the true response rate were 50%. The observation of at least 8 responses (8/20; 40% ORR) would be considered evidence to rule out a response rate of 25%. The exact power and type I error for this design are 87% and 10%, respectively.
6. Checkpoint refractory: In this cohort a true response rate of 25% or greater would be considered evidence of activity whereas a response rate of 5% or less (based on historical data) would not be considered of interest. With 20 patients, this study has 91% power to rule out a response rate of 5%, at the 1-sided 0.10 level if the true response rate were 25%. The observation of at least 3 responses (3/20; 15% ORR) would be considered evidence to rule out a response rate of 5%. The exact power and type I error for this design are 91% and 7.6%, respectively.

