Study Objectives	1. Primary objective is to estimate the clinical response as quantified by irRECIST 1.1 to hypofractionated radiotherapy with nelfinavir and anti-PD1/PDL1 immunotherapy. 2. Secondary objectives are to evaluate late toxicity, immune-related clinical responses and immune pharmacodynamic changes hypofractionated radiotherapy with nelfinavir and anti PD1/PDL1 immunotherapy
Diagnosis and Main Inclusion Criteria	Patients with previously untreated or previously treated metastatic melanoma, NSCLC, or renal cell carcinoma with bone, lung, liver, or subcutaneous or nodal involvement but without evidence of brain involvement. Patients who have previously been treated with radiation will be included in the study, so long as a suitable plan for treatment can be developed. Patients who have received prior immunotherapy will be included in the study and enrolled into a separate stratum.
Study product, dose, route, regimen	Hypofractionated Image Guided Radiation Therapy. Three fractions of 800cGy each given over 3-14 days. Pembrolizumab, Nivolumab, or Atezolizumab per standard dosing and schedule. Nelfinavir: 1250 mg PO BID administered for 7 – 14 days prior to start of immunotherapy, for a total of 11-12 weeks.
Duration of administration	Radiation treatment to be delivered over 3-14 days with concurrent Nelfinavir and Immunotherapy. Subjects will take nelfinavir for a total of 11-12 weeks. Immunotherapy will continue per the FDA-approved dosing schedule.
Reference Therapy	FDA-approved PD-1 or PD-L1 inhibitors
Number of trial subjects	The expected accrual rate = 30 pts/yr. The protocol is designed for a maximum total of 120 patients (10 patients per year for melanoma and 10 patients per year for NSCLC and 10 patients per year for RCC).
Study Duration	The expected total study duration is 4 to 4 1/2 years needed to complete accrual.
Statistical Methodology	This is a stratified phase II study of hypofractionated radiotherapy combined with immunotherapy for previously untreated or previously treated metastatic melanoma, NSCLC, and renal cell carcinoma patients. Phase II is stratified by histology and whether or not the patient has received prior immunotherapy. We will also collect serum for correlative studies.

Table of Contents

1.0	INTRODUCTION TO THE PROTOCOL	6
1.1	Introduction.....	6
1.2	Preclinical Data.....	7
1.3	Clinical Data to Date.....	10
1.4	Reference Therapy: PD-1 and PD-L1 Inhibitors.....	12
1.5	Dose Rationale	15
1.6	Other Agents.....	15

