
[figure not shown]
The primary objective of this clinical trial is to determine whether hypofractionated radiotherapy and PI-3k inhibition using Nelfinavir can improve upon standard-of-care immunotherapy by targeting the PD-1 receptor in melanoma, renal cell carcinoma, and non-small cell lung cancer. Since the time of this protocol's original development, the Food and Drug Administration has rapidly given approval to additional drugs that belong to the same class as nivolumab (PD1/PD-L1 inhibitors) with *some overlapping* clinical indications for melanoma, non-small cell lung cancer, and renal cell carcinoma. These drugs currently include pembrolizumab [49-52] for melanoma and NSCLC, atezolizumab [53-60] for NSCLC, with FDA-approval pending for durvalumab [61-64]. These drugs all have similar clinical efficacy

and toxicity profiles to nivolumab [65-69] in the setting of melanoma (response rates 30-40%) [50, 52], non-small cell lung cancer (response rates 30-40%) [49, 53], and renal cell carcinoma (~25%) [70]. These drugs have varying treatment schedules allowing the physician and patient greater flexibility to tailor the immunotherapy regimen to their needs and circumstances.

Currently, there is no direct comparison data to indicate the superiority of one PD1/PDL1 antibody over another. The available agents are considered equivalent in their applicable settings. There is no rigid order of prioritization. In the absence of other factors, our institution plans to select pembrolizumab as the first-choice agent, due to its preferred 3-week scheduling over the 2-week scheduling of nivolumab, for melanoma and NSCLC patients enrolled on this clinical trial. Pembrolizumab and nivolumab are both preferred over atezolizumab because they have been more extensively studied and characterized. Certain factors arise that may lead to the selection of nivolumab (for melanoma or NSCLC) or atezolizumab (NSCLC), including a patient's individual insurance approval as well as the continuation of previously-started PD1 therapy among patients in the PD1 refractory cohort. See *Section 3.1 Immunotherapy Reference Therapy*

Nelfinavir: There are ample data available regarding the use of NFV in humans [37]. The following is an excerpt of the key features.

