2.2 Study Design

This is a multi-cohort phase II trial of nelfinavir with hypofractionated radiotherapy and immunotherapy in advanced non-small cell lung carcinoma (NSCLC), melanoma, and renal carcinoma (RCC). The cohorts will be based upon histology (Melanoma vs NSCLC vs RCC) and prior immune checkpoint therapy (naïve vs refractory).

* See *Selection Pathway Section 3.1*

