4.0 SUBJECT ELIGIBILITY

4.1 Inclusion Criteria

4.1.1 Disease eligibility and Stage

- Histologically confirmed diagnosis of melanoma, NSCLC, or renal carcinoma.
- Previously treated or previously untreated stage IV melanoma, stage IV or recurrent lung cancer, and metastatic renal cancer by AJCC staging criteria
- Presence of a lesion that is suitable for hypofractionated radiotherapy

- 4.1.2 Disease measurement specifications
- 4.1.3 **Subjects must have measurable disease by RECIST criteria independent of the lesion to be irradiated.** Prior checkpoint inhibitor immunotherapy or chemotherapy is allowed as long as the last dose was received >14 days prior to enrollment.
- 4.1.4 Age ≥ 18
- 4.1.5 ECOG 0-2 (see Appendix 14.2)
- 4.1.6 Acceptable marrow function and hematologic indices for PD1/PDL1 immune checkpoint inhibitor and nelfinavir as per standard of care.
- 4.1.7 Ability to understand and the willingness to sign a written informed consent document.

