11.2 Analysis Plan

The primary analysis within each cohort will done on patients who receive at least one dose of nelfinavir, and anti-PD-1/PD-L1 therapy and at least one fraction of radiation. The safety analysis population will include all patients who receive at least one dose of any of the study drugs.

Binary endpoints (response, toxicity) will be summarized as proportions with associated 90% Clopper-Pearson confidence intervals. With 20 patients per cohort, binary proportions can be estimated to within 18% with 90% confidence. Any toxicity with true prevalence of at least 10% is likely to be observed (with 88% probability).

The distribution of time-to-event endpoints will be estimated using the method of Kaplan-Meier to derive estimates for median times and percentages at landmark times (e.g. 6 months). Confidence intervals for median times will be estimated using the Brookmeyer-Crowley method and for landmark times will be calculated using Greenwood's formula and based on a log-log transformation applied on the survival function.

A logistic regression model will be used to assess the association between response and factors such as smoking within each cohort. These associations will be summarized by odds ratios and associated confidence intervals and p-values. A Cox regression model will be used to assess the association between time-to-event outcomes (PFS,OS) and factors within each cohort. Similarly, these associations will be summarized by hazard ratios and associated confidence intervals and p-values.

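### The previously treated cohorts are assigned by conflicting rules, but their 5% and 15% null response rates fit only disease refractory to anti-PD-1/PD-L1 therapy

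*Combined protocol and SAP*

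**What the plan says.** The readable text assigns the second cohort in each disease in four ways.

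- **Any prior immunotherapy.** The synopsis says so twice: "Patients who have received prior immunotherapy will be included in the study and enrolled into a separate stratum" (main inclusion criteria) and "Phase II is stratified by histology and whether or not the patient has received prior immunotherapy" (statistical methodology).
- **Prior checkpoint therapy.** Section 2.2 forms cohorts by "Melanoma vs NSCLC vs RCC) and prior immune checkpoint therapy", with the levels naïve and refractory.
- **Refractory to anti-PD-1/PD-L1.** Section 2.1.1 and the opening of Section 11.1 say this, the latter as "those with disease refractory to anti-PD-1/PD-L1 therapy". Section 1.4 uses the same label when it mentions "continuation of previously-started PD1 therapy among patients in the PD1 refractory cohort".
- **Exposure to anti-PD-1/PD-L1.** The sample-size paragraph of Section 11.1 counts the six cohorts as three diseases by two exposure groups. Section 11.3 contrasts naïve patients with those previously exposed.

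On eligibility, Section 4.1.3 says only: "Prior checkpoint inhibitor immunotherapy or chemotherapy is allowed as long as the last dose was received >14 days prior to enrollment". On the analysis set, Section 11.2 says: "The primary analysis within each cohort will done on patients who receive at least one dose of nelfinavir, and anti-PD-1/PD-L1 therapy", plus at least one fraction of radiation. Neither mentions progression on earlier treatment.

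The refractory tests in Section 11.1 are items 2 and 6 (NSCLC and RCC: null 5%, success at 3/20 or more) and item 4 (melanoma: "a response rate of 15% or less (based on historical data) would not be considered of interest", success at 5/20 or more).

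**The concern.** Each cohort is single-arm, so the historical null is the only comparator and has to describe the patients who are counted. The plan's own naïve nulls are 25% for NSCLC and RCC and 43% for melanoma. Nulls of 5% and 15% therefore suit only patients whose disease has already failed anti-PD-1/PD-L1 treatment.

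If the stratum is filled by the synopsis rule, two other kinds of patient may enter: those exposed to anti-PD-1/PD-L1 without progression, and those whose only earlier immunotherapy was of another class. If they respond more often than refractory patients, the test can succeed with no added benefit from the regimen, and 3/20 or 5/20 would no longer show activity in refractory disease. The cut-offs are low, so one or two such responders can decide a result.

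**Working it through.** **1. Where each kind of patient goes.** Here refractory is read as progression on earlier anti-PD-1/PD-L1 therapy, since no readable section defines it.

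| Earlier treatment | Synopsis | Section 2.2 | Refractory wording (2.1.1, 11.1) | Exposure wording (11.1, 11.3) |
|---|---|---|---|---|
| Anti-PD-1/PD-L1, progressed | Prior immunotherapy | Refractory | Refractory | Exposed |
| Anti-PD-1/PD-L1, not progressed | Prior immunotherapy | Neither level | Neither level | Exposed |
| Only another class, e.g. anti-CTLA-4 | Prior immunotherapy | Unclear: Section 1.1 discusses CTLA4 among checkpoint targets | Naïve | Not exposed |

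The rules agree only on the first row. Sections 4.2.1 and 4.2.4 remove some patients in the other rows (unrecovered adverse events, intolerance of the selected agent), but not all.

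**2. The plan's own figures.** Exact binomial, n = 20, success if X ≥ r.

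- NSCLC and RCC refractory, r = 3: P(X ≥ 3) is 0.0755 at 5% and 0.909 at 25%. The plan states 7.6% and 91%; the 0.05-point difference is immaterial.
- Melanoma refractory, r = 5: P(X ≥ 5) is 0.170 at 15% and 0.949 at 40%. The plan states 17% and 95%.

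The arithmetic is sound. The question is which patients the nulls describe.

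**3. Effect of mixing.** Let a share f of the cohort be non-refractory and respond at rate q with no added benefit from the regimen. The response rate with no benefit is p = p0 + f(q − p0). The documents give neither f nor q for this group, so both are assumptions. The highest q in each table is the plan's own naïve null.

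NSCLC and RCC: p0 = 5%, P(X ≥ 3), 7.5% with no mixing.

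| q | f = 10%: p, probability | f = 25%: p, probability |
|---|---|---|
| 10% | 5.5%, 9.4% | 6.25%, 12.6% |
| 15% | 6.0%, 11.5% | 7.5%, 18.6% |
| 25% | 7.0%, 16.1% | 10.0%, 32.3% |

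Melanoma: p0 = 15%, P(X ≥ 5), 17.0% with no mixing.

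| q | f = 10%: p, probability | f = 25%: p, probability |
|---|---|---|
| 20% | 15.5%, 18.8% | 16.25%, 21.5% |
| 30% | 16.5%, 22.5% | 18.75%, 31.6% |
| 43% | 17.8%, 27.7% | 22.0%, 45.8% |

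The 30% row is the lower end of the 30-40% that Section 1.4 gives for these drugs in melanoma. One of its two sources there is, by title, in ipilimumab-refractory melanoma, though the split between the sources is not given.

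**4. Fixed counts.** Fixing the number of non-refractory patients at 2 or 5 of 20, instead of a random mix, changes each figure by less than one percentage point.

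**The case against.** The strongest reply is that Sections 1.4, 2.1.1, 2.2 and 11.1 all say refractory, while the synopsis is a summary that speaks only of a separate stratum and sets no null. Section 4.1.3 is a washout rule, not a cohort rule. Much of this stands: refractory disease is plainly the intended target of these tests. But Section 11.1 also describes the same cohorts by exposure, as does Section 11.3, so the looseness is not confined to the synopsis. Nor does the word explain itself, since Section 6.7 accepts that progression on a first scan need not mean that treatment has failed.

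Second, the design figure in Section 2.2, the selection pathway in Section 3.1 and the schema in Section 14.1 could not be seen and may define cohort entry. That also stands. A reader might infer that the plan has no definition, or that non-refractory patients will certainly be enrolled; the documents support neither. A definition in a figure would still leave the readable rules in conflict.

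Third, the inflation can be small: 9.4% at 3/20 and 18.8% at 5/20 at the low end. A reader might take 32% and 46% as the true type I errors. They are the top of an assumed range.

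A reader might also suspect the 25% null for checkpoint-naïve NSCLC, because Section 1.4 gives 30-40% for this drug class. The documents do not show that null to be wrong. Section 1.1 reports 25-34% across tumour types, and the sources for 30-40% concern, by title, PD-L1-positive or previously treated NSCLC.

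**Conclusion.** The concern holds as a conflict in the readable text that reaches three of the six primary tests. The cohort rules disagree, only one of them fits the 5% and 15% nulls, and neither the readable eligibility criteria nor the primary analysis set screens out non-refractory patients.

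The bias is conditional: such patients must be counted, and must respond more often than refractory ones. Over shares of 10% to 25% and the rates tabulated, the chance of a false success runs from 9.4% to 32% for NSCLC and RCC (7.5% as designed), and from 19% to 46% for melanoma (17% as designed). The documents cannot narrow these ranges. This should be corrected before the refractory cohorts are analysed; sample sizes and cut-offs need no redesign on this account.

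**What to change.** Use one cohort rule throughout.

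1. State in Sections 11.1 and 11.2 that each refractory cohort's primary test counts only patients with documented progression on or after earlier anti-PD-1/PD-L1 therapy. The sponsor should state how progression is documented.
2. Align both synopsis statements, Section 2.2, and the exposure wording in Sections 11.1 and 11.3 with that rule.
3. Count patients whose only earlier immunotherapy was of another class as anti-PD-1/PD-L1-naïve, as Section 11.1 implies.
4. Report exposed but non-refractory patients descriptively, outside the primary tests, and state whether they fall within the 120-patient maximum.
5. Record the class of earlier immunotherapy and any progression on it at registration.

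**Cost.** Wording changes and one registration item, with somewhat slower accrual to the refractory cohorts. The six cohorts of 20 already use all 120 places. If the maximum is kept, each patient under step 4 takes a place, and a refractory test may have fewer than 20.

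Step 3 could make the melanoma-naïve test more conservative and cost some power. As an illustration, suppose 25% of that cohort had only another class and responded at 30% or 40%. The rate with no benefit is then 0.43 − 0.25 × 0.13 = 0.3975 or 0.43 − 0.25 × 0.03 = 0.4225, and P(X ≥ 11) falls from 19.5% to 12% or 18%.

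### The two melanoma success thresholds (11/20 and 5/20) have type I errors of 19.5% and 17%, not the one-sided 0.10 the plan states

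*Combined protocol and SAP*

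**What the plan says.** Section 11.1 sets the design for every cohort: "The total sample size for this study is 20 patients in each of the 6 cohorts", and "The design within each cohort is a single arm, single stage design". Each cohort then has a null rate, a target rate, a headline power at a nominal level, a minimum number of responses that counts as success, and the exact operating characteristics of that rule.

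For checkpoint-naive melanoma (item 3) the null rate is 43% and the target is given as: "In this cohort a true response rate of 68% or greater would be considered evidence of activity". The headline claim is that "this study has 84% power to rule out a response rate of 43%, at the 1-sided 0.10 level". The decision rule is: "The observation of at least 11 responses (11/20; 55% ORR) would be considered evidence". The exact characteristics are: "The exact power and type I error for this design are 93% and 19.5%, respectively".

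For checkpoint-refractory melanoma (item 4) the null rate is 15%, the target is 40%, and the headline is 90% power at the same one-sided 0.10 level. The rule is: "The observation of at least 5 responses (5/20; 25% ORR) would be considered evidence". The exact characteristics are: "The exact power and type I error for this design are 95% and 17%, respectively".

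The NSCLC and RCC cohorts follow the same template. Their printed exact type I errors are 10% (8/20, naive) and 7.6% (3/20, refractory).

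**The concern.** Within each melanoma item, the nominal level and the decision rule describe different tests. A rule with a 19.5% or 17% chance of success under the null cannot be a 0.10-level test, and nothing in the plan says that a looser standard was meant for melanoma.

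The threshold is the only rule in the plan for declaring a cohort positive on the primary endpoint. With exactly 11 responses in the naive cohort, or exactly 5 in the refractory cohort, the threshold sentence declares activity while the stated level does not support it. The design is single-arm against historical rates, so no concurrent control would expose a false positive. Melanoma would also be judged by an easier standard than NSCLC and RCC in the same report.

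**Working it through.** **Inputs (section 11.1).** n = 20 per cohort, single stage. Melanoma naive: p0 = 0.43, p1 = 0.68, success at r = 11. Melanoma refractory: p0 = 0.15, p1 = 0.40, success at r = 5. Nominal level: one-sided 0.10.

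**Formula.** For X ~ Binomial(20, p), P(X ≥ r | p) = Σ (k = r to 20) C(20, k) p^k (1 − p)^(20 − k). Type I error is this tail at p0, and power is the tail at p1.

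**Step 1: the plan's own figures.**

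| Rule | Type I error | Printed | Power | Printed |
|---|---|---|---|---|
| Naive, ≥ 11/20 | 0.1949 | 19.5% | 0.9281 | 93% |
| Refractory, ≥ 5/20 | 0.1702 | 17% | 0.9490 | 95% |

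All four reproduce. Against 0.10 the ratios are 0.1949/0.10 = 1.9 and 0.1702/0.10 = 1.7.

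**Step 2: does n = 20 force this?** Raise each threshold by one response.

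| Rule | Type I error | Power |
|---|---|---|
| Naive, ≥ 12/20 | 0.0958 | 0.8432 |
| Refractory, ≥ 6/20 | 0.0673 | 0.8744 |

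Both meet 0.10 at the same sample size. Exact power falls by 92.8 − 84.3 = 8.5 points (naive) and 94.9 − 87.4 = 7.5 points (refractory).

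**Step 3: the other four cohorts.** NSCLC and RCC naive (≥ 8/20, 0.25 against 0.50): type I error 0.1018, power 0.868. NSCLC and RCC refractory (≥ 3/20, 0.05 against 0.25): type I error 0.0755, power 0.909. These are at or near the nominal level; only the melanoma rules depart from it materially.

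**Step 4: the same result as a confidence bound.** A one-sided 0.10 test rejects p0 when the exact one-sided 90% lower bound exceeds p0.

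| Responses | Lower bound | Null rate | Excluded? |
|---|---|---|---|
| 11/20 | 38.5% | 43% | No |
| 12/20 | 43.3% | 43% | Yes |
| 5/20 | 12.7% | 15% | No |
| 6/20 | 16.6% | 15% | Yes |

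**Step 5: effect on false-positive calls, assuming independent cohorts and no benefit in any.**

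- Two melanoma cohorts, at least one false call: 1 − (0.8051 × 0.8298) = 33.2% as written; 1 − (0.9042 × 0.9327) = 15.7% with 12/20 and 6/20.
- All six cohorts: 1 − (0.8051 × 0.8298 × 0.8982² × 0.9245²) = 53.9% as written; replacing the first two factors with 0.9042 × 0.9327 gives 41.8%.

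**Step 6: where the headline powers come from.** They need not be exact powers. The arcsine approximation, Φ(2√n(arcsin√p1 − arcsin√p0) − 1.2816), gives Φ(0.994) = 0.840 for naive and Φ(1.286) = 0.901 for refractory, which match the stated 84% and 90%. The stated 84% therefore does not by itself show that 12/20 was the intended rule.

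**The case against.** The strongest reply is that nothing is hidden. The plan prints the true type I error directly after each threshold, and the figures are correct. The documents also cannot show whether 11/20 and 5/20 were deliberate, with the 0.10 wording carried over from the template, or the reverse. Both points stand. They make this an unreconciled contradiction rather than a miscalculation, but they do not say which statement governs.

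A second reply is that strict compliance with 0.10 is not the plan's own standard, since the 8/20 rule sits at 10.18%. That is fair as far as it goes. A rule 0.2 points over the level is rounding; rules 9.5 and 7 points over are not.

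A third is that the six-cohort figure is peripheral. The cohorts are evaluated separately, no study-wide error rate is claimed, and most of the 53.9% remains after correction. This also stands, and the conclusion rests on the per-cohort rates.

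Finally, the stakes are limited. There is no interim efficacy rule in 11.1, so the thresholds do not affect any patient's enrolment or treatment. Section 11.2 also reports 90% Clopper-Pearson intervals, whose lower limits at 11/20 and 5/20 are 34.7% and 10.4%, so a reader would see the null rate inside the interval. That interval is not a substitute for a coherent rule, however. It is stricter than a one-sided 0.10 test and would include the null even at 12/20 (39.4%) and 6/20 (14.0%). The threshold still decides the stated conclusion.

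**Conclusion.** The concern holds. In two of six cohorts the primary-endpoint decision rule does not have its stated level: 19.5% and 17.0% instead of 10%. Nothing elsewhere in the plan reconciles the two, and thresholds that meet the level exist at the same sample size. The result needs only the plan's own n, null rates and thresholds and exact binomial probabilities. Independence between cohorts matters only for the multi-cohort figures, which are context. Because the rule determines whether melanoma is declared a success, this must be settled before response is analysed.

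**What to change.** The sponsor should state which was intended and make section 11.1 consistent, in one of two ways.

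- **Keep the 0.10 level.** Naive melanoma: at least 12 responses (12/20; 60%), exact power 84%, type I error 9.6%. Refractory melanoma: at least 6 responses (6/20; 30%), exact power 87%, type I error 6.7%, with the headline 90% replaced by 87%.
- **Keep 11/20 and 5/20.** Delete the 0.10, 84% and 90% statements for these cohorts, state a one-sided 0.20 level with the printed exact values, and justify the looser standard relative to NSCLC and RCC.

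Neither option adds patients. The first lowers exact power from 93% to 84% and from 95% to 87%, close to what the headlines already claim. The second costs no power but openly accepts about twice the false-positive rate.

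The edit is short, but the first option changes the primary decision rule, so it needs a dated amendment. Section 8.0 refers to re-opening enrolment in 2019 or 2020, so patients may already have been treated. Section 9.2 defers the formal response reads to the end of accrual, and the amendment should precede them so that the choice cannot depend on the data.
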